### **7.3.3 Withdrawal of patients from treatment or study**

#### **7.3.3.1 Withdrawal from treatment**

A patient should be withdrawn from the study treatment if, in the opinion of the investigator, it is medically necessary, or if it is the wish of the patient's primary caregiver(s). During the informed consent process, the investigator will clarify that it is essential for the patient's safety to be willing to comply with the study protocol requirements, including study safety and immunogenicity assessments following a potential withdrawal of study treatment.

When a patient is withdrawn from study treatment, the date and time of the last SOBI003 infusion and the date and reason for treatment withdrawal should be clearly described in the relevant sections of the case report form (CRF). If a patient is removed from treatment because of an AE, the reason for treatment withdrawal should always be stated as 'AE' irrespective of whether this was the investigator's or the patient's primary caregiver(s) decision.

After treatment withdrawal, efficacy, safety, immunogenicity and PK assessments should be completed as soon as possible and repeated 30 to 40 days after the last SOBI003 administration, as specified for "Early Termination" in the Schedule of Events (Table 2).

When possible, study assessments (excluding SOBI003 infusion) of Weeks 38, 52, 78 and 104 should continue in accordance with the Schedule of Events (Table 2) in order to collect continuous immunogenicity, safety and efficacy data for study patients following withdrawn treatment. Additional safety assessments will be performed at the discretion of the investigator, as warranted by the AE(s) leading to treatment withdrawal.

A patient that is withdrawn from study treatment due to an AE, should be followed up until the AE(s) leading to treatment withdrawal are either resolved or have stabilized even after the patient's participation in the study is over. Each clinically significant abnormal laboratory value or other clinically meaningful abnormality should be followed until the abnormality resolves or until a decision is made that it is not likely to resolve. Should the 30 to 40-day post last infusion be ADA-positive, then the ADA titer will be determined and ADA samplings will continue at approximately monthly basis until the ADAs have disappeared or titers have stabilized at a lower level. Every time an ADA sample is taken, a corresponding PK assessment is done.

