#### 7.5.1.8 Early withdrawal from treatment/study

If the patient is withdrawn from study treatment, the patient should be examined as soon as possible after making the withdrawal decision. AEs and use of concomitant medications are captured. Blood is collected for safety laboratory, HS, immunogenicity and PK assessments. Urine is collected for safety laboratory and HS assessments.

Vital signs are assessed, and a neurological and a physical examination are performed. An ECG is conducted, and height, weight and head circumference are obtained.

The VABS-II is assessed by parent/caregiver (refer to Section 7.5.3.2). The parent/caregiver completes the PedsQL questionnaire.

Based on the patient's developmental age, as determined by the VABS-II score, the BSID-III and/or KABC-II tests are conducted for assessment of neurocognition, language and motor function (see Sections 7.5.3.1, 7.5.3.2, and 7.5.3.6, respectively). If *both* BSID-III and KABC-II should be assessed, then the BSID-III should be administered 2 days prior to the completion of KABC-II.

When possible, study assessments (excluding SOBI003 infusion) of Weeks 38, 52, 78 and 104 should continue in accordance with the Schedule of Events. At minimum, the Early

Termination assessments should be repeated 30 to 40 days after the last SOBI003 administration. Patients with ADA-positive samples should continue to be followed in accordance with Sections 7.5.4.3 and 7.5.5.1.

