treatment interaction as fixed factors, baseline age as covariate and an unstructured covariance matrix will be used to estimate the covariance pattern. The primary efficacy analysis set will thus consist of all patients included in this extension study (patients treated with SOBI003) and 14 patients from the NH study (untreated patients). The null hypothesis of no treatment effect will be tested with a significance test for the treatment\*time-effect, in the second step of the multiple testing procedure (see Section 9.4.5) The difference between 104 weeks and baseline will be used as the contrast of interest for the test.

All missing DQ values will be imputed. For a patient who stops treatment, let  $tp$  denote the turning point, i.e. the time point when the patient stops treatment. The patient's assessments as well as the time points for prediction are classified as being on either side of the turning point or at the turning point: prior to  $tp$ , at  $tp$ , or after  $tp$ . For patients who does not stop treatment, let  $tp = \infty$ , i.e. every time point is considered as prior to the  $tp$ . Let  $v$  denote a missing value to be imputed for a patient. The imputations will be based on two categories of predictions.

1) If the patient has two or more observations on the same side of  $tp$  as  $v$  (including a possible observation at  $tp$ ), then  $v$  is considered as *exclusively patient-predictable* ( $p_1$ ), i.e. it can be predicted by simple linear regression based only on the patient's data (intra -or extra-polation). On the other hand, if only one or zero observations exists on the same side of  $tp$  (from the particular patient) as  $v$  (including a possible observation at  $tp$ ), then it is considered as *non-predictable exclusively* from the patient's data.

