All missing values will be imputed. For a patients who stops treatment, let tp denote the turning point, i.e., the time point when the patient stops treatment. The patient's assessments as well as the time points for prediction are classified as being on either side of the turning point or at the turning point: prior to tp , at tp , or after tp . For patients who does not stop treatment, let $tp = \infty$, i.e., every time point is considered as prior to the tp . Let v denote a missing value to be imputed for a patient. The imputations will be based on two categories of predictions.

1). If the patient has two or more observations on the same side of tp as v (including a possible observation at tp), then v is considered as *exclusively patient-predictable* (p_1), i.e., it can be predicted by simple linear regression based only on the patient's data (intra-or extrapolation). On the other hand, if only one or zero observations exists on the same side of tp (from the particular patient) as v (including a possible observation at tp), then it is considered as *non-predictable exclusively* from the patient's data.

2) The other type of prediction (p_2), will be calculated by the use of a population derived slope, estimated based on the repeated measures model in Section 14.1 (without imputations), and a patient observation. There will be two cases: If the patient has one or more observations on the same side of tp as v (including a possible observation at tp), then the nearest observation will be used together with a slope, which is based on the population (treated or untreated) of the same

status as the side of tp where the prediction time point is situated, as well as the interval relative the visits which contain the prediction time point. The other case is when there is no observation on the same side of tp as v (and no observation at tp). In this case, a prediction at tp will first be calculated, based on the same method as described above (under 2) but on the other side of tp , i.e., the nearest observation relative tp on the other side of tp will be used together with a slope based on the population (treated or untreated) of the same status as the side of tp where this nearest observation time point is situated, as well as the interval relative the visits which contain the tp . This prediction at the tp is in then used to predict v as described under the first case (under 2).

For each missing value v , the following algorithm is used to impute v by i .

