
If p_1 does not exist, then p_2 is used, i.e., $i = p_2$.

Otherwise, a weighted average will be used for the imputation: $i = w_1 p_1 + w_2 p_2$, where $w_1 = \exp(-\lambda \ln(2)/3)$ and $w_2 = 1 - \exp(-\lambda \ln(2)/3)$ and λ is the distance in months between the time point for prediction and the nearest available non-missing patient assessment time point. The exponential function is motivated by an exponential decrease of relevance of individual patient data relative to population data with increasing time, and the coefficient $\ln(2)/3$ is chosen such that population data reach the same weight as individual patient data after 75 % of the distance between two visits, i.e., three months. When individual patient data is available near a missed visit, the patient data weight is near 100 %, and when the distance is near one year on the other hand, the individual patient data weight has decreased to nearly 6 %.

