14.1.1 Sensitivity analyses of the DQ endpoint

In order to assess the sensitivity of the model, the DQ model described in Section 14.1 will

- Only use non-missing values, i.e., no imputations will be performed
- Be extended with a triple interaction factor time*treatment*baseline age
- Use DQ = 0 for missing DQ values

An additional sensitivity analysis will be a tipping point analysis: All combinations of DQ values (n_{UN}, n_T) where $n_{UN}, n_T \in \{0,1,2,\dots,100\}$ are substituted for missings in the untreated arm and the treated arm respectively. P-values will be calculated for each combination.

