14.3 Multiple comparison procedure

A hierarchical approach will be used for the key secondary co-endpoints.

The primary analysis will be based on a 2-sided test using a significance level of 0.05. A stepwise sequential testing procedure will be used to ensure a multiple level of significance of 0.05.

- 1st step: The null hypothesis of no difference between the treatments with respect to the reduction from baseline HS in CSF at 24 months will be tested using a significance level of 0.05. If the null hypothesis is rejected, then it will be concluded that SOBI003 reduces HS. Furthermore, the 2nd step of the sequential testing procedure will be performed.
- 2nd step: The null hypothesis of no difference between the treatments with respect to the change in DQ score at 24 months will be tested using a significance level of 0.05. If the null hypothesis is rejected, it will be concluded that Sobi 003 improves cognitive function as compared to untreated patients.

This multiple comparison procedure controls that the multiple level of significance is no more than 5 %.

Formally, the second confirmatory step will only be valid after the 1st step has been successfully met.

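### Missing DQ scores are filled with a single noise-free prediction and tested as measured, so the 5% level of step 2 is not assured if children still on treatment lack a Week 104 score

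*SAP*

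**What the plan says.** Protocol 9.4.4.1 states "All missing DQ values will be imputed", and SAP 14.1 gives the same algorithm. Each gap receives one value. If the child has two or more scores on the same side of the stopping time, a straight line through them gives p1. A second prediction, p2, uses a population slope, chosen by whether the gap falls before or after the child stopped treatment: "the nearest observation will be used together with a slope, which is based on the population (treated or untreated) of the same". When p1 exists, "Otherwise, a weighted average will be used for the imputation", with a weight on p1 that decays with distance; otherwise p2 is used alone. A child who never stops treatment is given an infinite stopping time, so every gap in that child is filled with the treated slope.

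The Week 104 minus baseline contrast from the repeated measures model on the filled data is step 2 of the hierarchy. SAP 14.3 says "This multiple comparison procedure controls that the multiple level of significance is no more than 5" percent, and adds: "Formally, the second confirmatory step will only be valid after the 1st step has been successfully met". The model without imputation ("Only use non-missing values, i.e., no imputations will be performed") appears in SAP 14.1.1 as a sensitivity analysis.

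**The concern.** The fill adds no residual draw and no uncertainty in the estimated slope, and neither document mentions multiple imputation or a variance or degrees-of-freedom correction. A filled Week 104 score contains no new measurement of the second year. It is largely the child's Week 52 score plus a slope learned from the other children, yet the model counts it as one more independent observation. The fixed-sequence procedure controls the overall level only if each component test has its own 5% level.

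With about 9 treated and 14 control children, one filled score is a ninth of the treated arm. The step 2 conclusion would be that SOBI003 improves cognition. SAP 17 plans identical DQ methods for the primary analysis of the phase 3 study, so the weakness would carry forward.

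**Working it through.** 1. **Inputs from the documents.** 14 controls with mean decline 30.4 (SD 12.1); 9 treated with planned decline 9.8, SD 13.0 (SAP 7.1); 9–12 treated planned (Protocol synopsis); two-sided 0.05 (SAP 14.3); model and imputation rule (SAP 14.1).

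2. **Inputs assumed.** The documents give no missing-data rate and no within-child correlation. I took SD 13.0 as the SD of the 104-week change, a Week 52/Week 104 change correlation of 0.5–0.7, and a Week 52 change SD of 9.2–13. Week 104 scores are missing at random among treated children who have a Week 52 score, and controls are complete. Other covariance shapes (independent increments, compound symmetry, random slope plus noise) gave similar results.

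3. **The plan's own figures.**
   - HS: change 0.8 × 5.2 = 4.16. With SD 1.8 at both visits, the SD of change is 1.8 × √(2 × 0.9) = 2.41. A paired t test with n = 9 then has power 99.4%, which matches the stated 99%.
   - DQ: SE = 13 × √(1/9 + 1/14) = 5.55, difference 30.4 − 9.8 = 20.6, power 94% by t test. The stated figure of at least 80% is met.
   - With nothing missing, simulated type I error is 4.8–5.2%, so the 5% level reproduces.

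4. **What the fill does.** At 12 months from the nearest score, w1 = 2^(−12/3) = 0.0625. With p1 = 2·Y52 − Y0 and p2 = Y52 + b, where b is the estimated treated slope, the filled change from baseline is 1.0625·(Y52 − Y0) + 0.9375·b.
   - If the Week 52 change SD is 9.2, the child-specific part has SD 1.0625 × 9.2 = 9.8, against 13 for a measured change. If it is 13, that part has SD 13.8, so reduced spread is not the whole mechanism.
   - In both cases b comes largely from the other treated children. Its error is shared between filled and measured values, and the test treats them as independent.

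5. **Simulation with no treatment effect.** Filled data were analysed as change on arm and baseline age, which equals the unstructured-model contrast on complete data. Main runs used 40,000 replicates per setting; the ranges also span separate runs.

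| Week 104 missing, on treatment | Type I error, 9 treated | SE too small by, 9 treated | Type I error, 12 treated |
|---|---|---|---|
| 0 | 4.8–5.2% | none | about 5.0% |
| 1 | 5.3–5.9% | 2–4% | 5.1–5.8% |
| 2 | 6.1–7.4% | 5–8% | 5.7–6.2% |
| 3 | 6.6–8.6% | 7–13% | 6.5–7.0% |

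   As an example, in the random-slope setting with 3 of 9 missing the mean model SE is 5.49 and the true SD of the estimate 6.11, a ratio of 0.90. Smaller runs of 10,000 replicates spread the 1-of-9 row to 5.2–6.3%. If 2 of 9 lack both Week 52 and Week 104, type I error is 8.1–8.7%.

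6. **Children who stop treatment.** They are filled with the untreated slope, which pulls the arms together.
   - Stop at Week 52, 1–3 of 9: 3.1–4.9% with no later score, and 3.5–5.2% with a repeat score 35 days later.
   - Stop at about months 16–22, with assumed score noise SD 6: about 4.9–6.0%.
   - Mixed: one on-treatment gap plus one stop at Week 52, 5.0–5.7%; two plus one, 5.7–6.7%.

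7. **Role of step 1.** With HS power near 99%, step 1 filters almost nothing when HS falls but DQ does not benefit. The overall level is then close to that of step 2.

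**The case against.** **The trigger is narrow.** It needs a child still receiving infusions who has no usable Week 104 score. Protocol 7.1 keeps infusions in efficacy-assessment weeks at the main site, Table 7 schedules the test within that week, SAP 14.1 allows two weeks either way, and Protocol 7.5.1.7 avoids dose changes in Weeks 100–104. Nothing in the documents predicts two or three such gaps among nine children. This stands, and it is why the level is called not assured rather than wrong.

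**The study is exploratory and sensitivity analyses exist.** Safety is the primary endpoint and the sample size is not statistically based. The no-imputation model would reveal a result that depends on filled values. That is fair, but SAP 14.3 treats step 2 as confirmatory and the decision rests on the filled data. The zero-imputation and tipping-point analyses also insert fixed values.

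**The sentence in SAP 14.3 is about test ordering.** This also stands. The fixed sequence is sound if its component tests are valid, and the sentence makes no claim about imputation. The point is only that it depends on a valid step 2.

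**Late scores.** A reader might infer that a score outside the two-week window is discarded even as the child's nearest observation. SAP 14.1 sets it to missing, but also says that patient data close to a missed visit carry almost full weight. With DQ visits a year apart, that points to using such scores. For a score 16 days late (0.53 months) the weight is 2^(−0.53/3) = 0.89, and type I error is 4.7–5.4% with 1–3 such children. This is not a defect.

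**Conclusion.** The point holds in limited form and should be fixed. As written, the standard error of the step 2 contrast is too small whenever a child still on treatment has a filled Week 104 score. The effect is nil with no gap, small with one, and material with two or three of nine; it is smaller with 12 treated. The direction follows from the algorithm. The size rests on the assumed correlations, SDs and missingness in the working.

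Three stronger readings are not supported:

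- That the step 2 test is invalid as it stands. With complete Week 104 data it has its 5% level.
- That the rule inflates error for every missing child. For a stop around Week 52 it is near or below 5%. For later stops it can reach about 6% under assumed score noise. Protocol 7.3.3.1 asks that assessments "should be completed as soon as possible and repeated 30 to 40 days after the last SOBI003 administration", and Protocol 7.5.1.8 says that, as a minimum, the "Termination assessments should be repeated 30 to 40 days after the last SOBI003 administration", so a score after stopping is often likely.
- That control scores are also filled. Protocol 9.4.4.1 describes 14 controls followed for 24 months, and nothing shows a missing control score.

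**What to change.** In SAP 14.1 and Protocol 9.4.4.1, keep the turning-point rule. For gaps in children still on treatment, replace the single value by proper multiple imputation: draw the slope parameters and residual variance, add a residual draw, and combine with Rubin's rules and small-sample degrees of freedom. Leave the post-stop fill as it is, and keep the no-imputation repeated measures model as the sensitivity analysis. Carry the change into the phase 3 analysis described in SAP 17.

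**Effect.** With 40 imputations, type I error for on-treatment gaps is 4.3–5.0%, 4.0–4.6% and 3.7–4.2% with 1, 2 and 3 of 9 missing; a separate run with 20 draws gave 3.5–5.2% with 2 or 3 missing. In mixed patterns of gaps and stops, with draws limited to on-treatment gaps, it is 3.3–4.7%. The possible small excess for late stops remains.

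**Cost.** Wording and some programming. With 2 of 9 missing, the 95% CI half-width rises from 11.4–11.8 to 12.6–13.1 DQ points (about 8–14% wider). Power at the planned effect, 93% in simulation with nothing missing, falls by about 1–2, 2–5 and 4–9 points with 1, 2 and 3 missing.

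**Why not impute stoppers the same way.** Multiple imputation after stopping lowers type I error to 0.7–3.7% for 1–3 stoppers and costs up to 22 power points. In mixed patterns the limited version keeps power at 80–89%, against 72–88% for full multiple imputation.

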14.1.1 Sensitivity analyses of the DQ endpoint

In order to assess the sensitivity of the model, the DQ model described in Section 14.1 will

- Only use non-missing values, i.e., no imputations will be performed
- Be extended with a triple interaction factor time*treatment*baseline age
- Use DQ = 0 for missing DQ values

An additional sensitivity analysis will be a tipping point analysis: All combinations of DQ values (n_{UN}, n_T) where $n_{UN}, n_T \in \{0,1,2,\dots,100\}$ are substituted for missings in the untreated arm and the treated arm respectively. P-values will be calculated for each combination.

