#### **9.4.10 Handling of missing data**

All missing DQ values will be imputed. A sensitivity analysis will be performed where no imputations are performed, but all values are used: If a patient has a missing DQ score in any assessment, then the same patient's non-missing scores will be used in the repeated measures model (see Section 9.4.4). The repeated measures model handles missing values based on the MAR assumption. One further sensitivity analysis will address this assumption based on zero imputations. Another sensitivity analysis for this purpose will be a tipping point analysis.

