5.2 Analyses and reporting

All final, planned, analyses identified in the protocol and in this SAP will be performed only after the last patient has completed the study.

Any post-hoc analyses included in the CSR, which were not identified in this SAP, will be clearly identified as such in the relevant section of the CSR.

For each patient in the study, all the associated safety and efficacy data in the SOBI003-001 study will be pooled and presented together with the SOBI003-002 study. Thus the SOBI003-001 study and the SOBI003-002 study are considered as a single, unified entity.

6 Estimands

There will be a de facto estimand in the study, which is the primary estimand for the evaluation of efficacy. The estimand is the change in

- cognitive decline in all the patients from the population captured by the inclusion and exclusion criteria (see Section 4.2.1 and Section 4.2.2) and the part of the NH population with a rapid progressive disease having a baseline age of 12 to 72 months, irrespectively of other medications used and adherence to treatment, and estimated by a repeated measures model of the change from baseline in DQ as described in Section 14.1.

- decline in HS levels in CSF in all the patients from the population captured by the inclusion and exclusion criteria (see Section 4.2.1 and Section 4.2.2) irrespectively of other medications used and adherence to treatment, and estimated by a repeated measures model of the change from baseline in HS as described in Section 14.1.

To address foreseeable inter-current events, such as drop-outs, all missing values will be imputed (see Section 14.1) in accordance with the treatment policy principle. A sensitivity analysis will be performed where no imputations are performed, but all values are used: If a patient has a missing value in any assessment, then the same patient's non-missing scores will be used in the repeated measures model. The repeated measures model (see Section 14.1) handles missing values based on the missing at random (MAR) assumption. One further sensitivity analysis for DQ will address this assumption based on zero imputations (see Section 14.1.1), the rationale being that the patients not assessed are those expected to have a severe DQ decline. Other sensitivity analyses for this purpose will be tipping point analyses, see Section 14.1.1.

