Furthermore, a principal strata analysis will be performed where only patients without protocol violations will be analyzed according (see Section 14.1.2). In particular patients who did not comply with the dosing scheme but continued the study will be excluded from the analysis. Thus the principal strata will be approximated by the clinical per protocol subset of FAS.

7 Sample size determination

7.1 Change from baseline in DQ score and in HS levels in CSF at 104 weeks

All patients completing the FIH study will be offered to continue into this extension study and the number of patients in the extension study is thus not based on statistical grounds.

However, the 14 patients in the natural history study that will be used as an external control group had a mean baseline DQ of 58.9 points and declined with a mean of 30.4 (SD=12.1) DQ points during 104 weeks. Therefore, assuming very high likelihood of showing significant decrease in HS (with baseline mean of 5.2, std 1.8, correlation of 0.1 and a decrease of 80 % the power is 99 %), with 9 patients treated with SOBI003, the power to demonstrate an improvement in cognitive function is at least 80 % if the decline is reduced from 30.4 to 9.8 DQ points (SD=13.0) and the reduction is homogeneous across age.

8 Analysis sets

The following analysis sets will be used in the statistical analyses and exploration of data.

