8.2 Full-analysis set

The full-analysis set (FAS) is the efficacy analysis set which will consist of all patients enrolled in this extension study, and all patients in the NH study with a rapid progressive disease having a baseline age of 12-72 months (in the DQ analyses).

All patients enrolled in this extension study and the FIH study will be treated as having received active treatment and patients from the NH study will be treated as having received no treatment. For each patient in the study, all the associated safety and efficacy data in the SOBI003-001 study will be pooled and presented together with the SOBI003-002 study.

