14.1 The DQ endpoint

One of the key secondary objectives is to assess the effect of SOBI003 on neurocognition, as compared to untreated MPS IIIA patients from a NH control. The key endpoint related to this

objective is the change from baseline in DQ of neurocognitive development at 104 weeks of treatment, and will be estimated by a model based contrast.

To address the efficacy objective, a repeated measure analysis will be utilized where DQ is the response variable and time, baseline age, time*baseline age and treatment*time are fixed effects and the dependency between observations within the same patient is represented by an unstructured variance-covariance matrix.

The time window is two weeks, i.e., if the assessment is more than two weeks too early or more than two weeks too late, then the DQ is set to missing for that assessment.

In the NH study, a simple linear regression model was used, i.e. with DQ as the response variable and the age of the child as dependent variable (Shapiro et al 2016). As the aim in this clinical development program is to demonstrate that treatment with SOBI003 is efficacious and the effect of treatment is dependent on the time the patient has been treated, this model needs to be adopted so that time and baseline age are factors rather than the actual age of the child (which is the sum of the baseline age and the time in study). The results from the NH study suggest that the decline in DQ is not linear across all ages, and an interaction term time*baseline age is planned to be included in the model to allow for such a non-linearity. Also an unstructured variance-covariance matrix is planned to be used to account for the dependency between observations within the same patient. As a further justification for the model, it should be noted that time, baseline age and time*baseline age are all significant factors in the NH study.

To represent the treatment effect without constraint to a specific relation across visits, a term treatment*time is planned to be included in the model. This effect is used to judge the treatment effect. The null hypothesis of no treatment effect will be tested with a significance test for the treatment*time-effect in the second step of the multiple testing procedure (see Section 14.3). The difference between 104 weeks and baseline will be used as the contrast of interest for the test.

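### The zero-imputation sensitivity analysis names no group, so missing natural-history scores are also set to zero, which mixes a credit to SOBI003 with the intended penalty

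*SAP*

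**What the plan says.** SAP 14.1.1 lists variants of the Section 14.1 DQ model as sensitivity analyses. One reads "Use DQ = 0 for missing DQ values". Section 14.1 compares SOBI003 with the NH controls through a treatment-by-time term, and SAP 8.2 places the eligible NH patients in the full analysis set for DQ. The test rests on one contrast: "The difference between 104 weeks and baseline will be used as the contrast of interest for the test".

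The reason for the zeros is in SAP 6 and again in SAP 9.1: "the rationale being that the patients not assessed are those expected to have a severe DQ decline". Protocol 9.3 gives the same reason, and Protocol 9.4.10 says "One further sensitivity analysis will address this assumption based on zero imputations". None of these places says which group or which visits receive the zero.

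Two other provisions bear on this:

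- SAP 14.1.1 also plans a tipping-point analysis. All pairs of values from 0 to 100 "are substituted for missings in the untreated arm and the treated arm respectively", with a P-value for each pair. No rule is given for reading the P-values.
- SAP 14.1 applies a two-week window. If an assessment falls outside it, "then the DQ is set to missing for that assessment". NH assessments are not exempted.

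**The concern.** The zero analysis is there to ask whether the conclusion survives if children who were not assessed had done very badly. For a claim of benefit against an external control, that question has force only for treated children. A zero in a treated child enlarges the treated decline and counts against the drug. A zero in a control enlarges the control decline and counts for it. A single rule covering both groups adds a penalty and a credit, and the net direction depends on where the gaps happen to fall.

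At stake is how the result is read. A finding reported as robust to zero imputation could owe part of that robustness to controls scored as having lost all measurable development.

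**Working it through.** **Inputs.** SAP 7.1 says the 14 NH patients "had a mean baseline DQ of 58.9 points and declined with a mean of 30.4 (SD=12.1) DQ points during 104 weeks". It takes 9 treated patients with a decline of 9.8 and an SD of 13.0. The documents give no count or rate of missing DQ scores in either group, and no baseline SD. Both are assumptions below.

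**The plan's own figure.** The planned difference is 30.4 − 9.8 = 20.6. With SD 13.0 and 9 versus 14 patients, the standard error is 13.0 × √(1/9 + 1/14) = 5.55. Two-sided power at 0.05 is 94.2% (noncentral t, 21 df) or 96.0% (normal approximation). The stated bound of at least 80% holds. The plan gives no figure for the zero-imputation analysis itself.

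**Shift caused by the zeros at Week 104.** Take the NH baseline mean for both groups, and let the missing children sit at their group mean.

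- Control mean at Week 104: 58.9 − 30.4 = 28.5. Each missing control adds 28.5/14 = 2.0 points toward SOBI003.
- Treated mean under the design effect: 58.9 − 9.8 = 49.1. Each missing treated score takes off 49.1/9 = 5.5 points (49.1/12 = 4.1 with 12 patients).
- Treated mean with no drug effect: 28.5. Each missing treated score takes off 28.5/9 = 3.2 points.

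Apparent benefit in DQ points, design effect first and no effect second:

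| Missing controls (of 14) | 0 treated missing | 1 treated missing | 2 treated missing |
|---|---|---|---|
| 0 | 20.6 / 0.0 | 15.1 / −3.2 | 9.7 / −6.3 |
| 1 | 22.6 / 2.0 | 17.2 / −1.1 | 11.7 / −4.3 |
| 2 | 24.7 / 4.1 | 19.2 / 0.9 | 13.8 / −2.3 |
| 3 | 26.7 / 6.1 | 21.3 / 2.9 | 15.8 / −0.2 |
| 4 | 28.7 / 8.1 | 23.3 / 5.0 | 17.8 / 1.8 |

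Three and four missing controls add 6.1 and 8.1 points, which is 30% and 40% of 20.6.

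**Break-even.** Under the design effect the net shift favours SOBI003 only if the missing fraction in the controls exceeds 49.1/28.5 = 1.72 times that on treatment. At equal fractions of 10%, 20% and 30%, the difference falls from 20.6 to 18.5, 16.5 and 14.4. With no drug effect, equal fractions cancel.

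**False benefit with no drug effect.** This was simulated as a pooled t test on change, 9 versus 14, change SD 12.1, counting results in the upper 2.5% tail. It approximates the planned repeated-measures model but is not that model.

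| Missing controls | 0 | 1 | 2 | 3 | 4 |
|---|---|---|---|---|---|
| None missing on treatment, baseline SD 15 | 2.5% | 3.5% | 5.2% | 8.2% | 13.0% |

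With baseline SD 25, three and four missing controls give about 5.6% and 8.5%. With one treated score missing and baseline SD 15, the range over 0 to 4 missing controls is about 0.4% to 3.5%. The rate can stay below 2.5% even where the table of shifts shows a bias toward SOBI003, because the zeros also inflate the variance.

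**Overlap with the tipping-point grid.** Setting every missing score in both groups to zero is the pair (0, 0) of that grid. As written, the separate zero analysis adds no new result.

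**The case against.** A reader might infer that this sensitivity analysis favours SOBI003 in general, or is anti-conservative whenever a control score is missing. The documents do not support either statement. The direction depends on the balance of missing data. One missing treated score outweighs two missing controls under the design effect (5.5 against 4.1 points). If no NH Week 104 score is missing, the rule can only hurt SOBI003. Missing NH scores are also not shown: Protocol 9.4.4.1 describes 14 patients followed for 24 months, and naming an untreated arm in the tipping-point text may be generic notation. The two-week window could create such gaps, but no count is given.

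The stated reason can also be defended for both groups. The plan does not call this a worst case. It says unassessed children are likely to have declined severely, which is plausible for untreated rapid progressors too. That makes the two-group rule a coherent assumption about the disease. It does not make it a test of the treatment claim.

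The strongest objection is the tipping-point grid. It varies the groups separately, and its cell with treated at 0 and untreated at about 28 is close to the corrected analysis; higher untreated values are harsher. The plan also includes the analysis without imputation. This stands and lowers the consequence. It does not remove the point: the grid has 101 × 101 cells and no reading rule, whereas the zero analysis is the named scenario with a stated rationale.

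**Conclusion.** The point holds in a limited form. The zero rule covers both groups as written, so it is not a clean stress test of the SOBI003 effect, and it leans toward SOBI003 when missing data are concentrated in the controls. The size is about 2.0 DQ points per missing control, against about 5.5 points the other way per missing treated score under the design effect.

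The false-benefit figures of up to about 13% require four missing controls, none missing on treatment and a baseline SD of 15. They should not be quoted without those conditions. They also describe a sensitivity analysis, which does not gate the hierarchical test in SAP 14.3.

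Severity is minor: this is one of several sensitivity analyses of a key secondary endpoint, and the tipping-point grid contains approximately the corrected scenario.

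**What to change.** In SAP 14.1.1, 6 and 9.1 and Protocol 9.3 and 9.4.10, write:

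> DQ = 0 for missing post-baseline DQ values in SOBI003-treated patients only; missing NH control values are handled as in the analysis without imputation (MAR).

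The word post-baseline matters because a zero at a missing baseline would turn the later score into a gain. Also report the number of missing DQ values by group and visit, so that a reader can see how much the analysis is being asked to carry.

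The change costs one clause and one small table. The sensitivity result may be less favourable. The design difference of 20.6 becomes 15.1, 9.7 or 4.2 with one, two or three of nine treated scores missing, however many NH scores are missing. With change SD 13, assumed baseline SD 15 to 25 and complete NH data, power falls from 94% to about 53–54% with one treated score missing and 14–19% with two. The analysis is then a demanding check, and a non-significant result from it should be read as such and not as a refutation.
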